#### **Rationale**

CAB+RPV LA is the first long acting intramuscular injection with an oral lead in, and differing doses for initiation and maintenance. While clinical studies have established the efficacy, safety and tolerability of Cabenuva®, this study will assess the utilization patterns, adherence and effectiveness of the regimen in real world clinical setting. Understanding patient characteristics and clinical outcomes of this regimen in heterogeneous population is of great importance to provide optimal care of PWH.

## 5. \*RESEARCH QUESTION AND OBJECTIVE(S)

The overall objective of this study is to describe characteristics and assess clinical outcomes among people with HIV in the Observational Pharmaco-Epidemiology Research and Analysis (OPERA®) cohort who receive CAB+RPV LA regimen.

#### **Primary Objectives:**

- 1. To describe baseline demographics, clinical characteristics and patterns of use among PWH receiving CAB+RPV LA at Year 3, Year 4, and Year 5 of availability
- 2. To assess the persistence, adherence and discontinuation among PWH receiving CAB+RPV LA at Year 3, Year 4, and Year 5 of availability
- 3. To assess virologic effectiveness among PWH receiving CAB+RPV LA at Year 3, Year 4, and Year 5 of availability
- 4. To assess factors associated with confirmed virologic failure among PWH receiving CAB+RPV LA regimen at Year 3, Year 4, and Year 5 of availability

#### **Secondary Objectives:**

- 1. Sub-group analyses by viral load (VL <50, ≥50copies/mL) at initiation, BMI (<30 and ≥30 kg/m²) at initiation and age (18-50, 50-64, ≥65 years) at initiation to assess characteristics, adherence, persistence, discontinuation and virologic effectiveness
- 2. To estimate the frequency of documented injection site reactions and hypersensitivity reactions among PWH receiving CAB+RPV LA injections at Year 3, Year 4, and Year 5 of availability
- 3. To compare baseline characteristics and treatment outcomes (persistence/discontinuation, adherence, maintaining virologic suppression, confirmed virologic failure) between oral ART and CAB+RPV LA use in PWH at Year 4 and Year 5 of availability
- 4. To describe baseline characteristics and treatment outcomes (persistence/discontinuation, adherence, virologic effectiveness) among PWH receiving CAB+RPV LA injections at Year 4 and Year 5, in subgroups of interest
  - a. Race/ethnicity (Non-Hispanic Black, Hispanic, Non-Hispanic White)
  - b. Sex/race (Non-Hispanic Black men, Hispanic men, Black women)
- 5. Among individuals with confirmed virologic failure (CVF): to describe HIV resistance and proviral testing at the time of CVF, as well as history of resistance and proviral DNA testing prior to CVF at Year 4 and Year 5 of availability

ViiV Healthcare Protocol Final 216990 – Amendment 2

- 6. Among individuals with confirmed virologic failure (CVF): to describe the ART regimens after CVF in OPERA at Year 4 and Year 5 of availability
  - a. To describe the baseline characteristics (demographic, clinical, treatment patterns) of ART regimen after CVF
  - b. To describe virologic response (suppression, non-response, confirmed virologic failure) to ART regimen after CVF

#### \*RESEARCH METHODS

## 6.1. Study Design

This is an observational study utilizing prospectively collected electronic health record (EHR) data obtained from the OPERA® cohort.

## 6.2. \*Study Population and Setting

People with HIV, 18 years or older, treatment experienced, and receiving CAB+RPV LA regimen or a new oral ART regimen recommended by the DHHS guidelines in the OPERA Cohort will be included.

## **Study Period:**

- o Year 3:
  - Period of eligibility: 21JAN2021-31DEC2023
  - Period of observation: 21JAN2021-29FEB2024
- O Year 4:
  - Period of eligibility: 21JAN2021-31DEC2024
  - Period of observation: 21JAN2021-28FEB2025
- o Year 5:
  - Period of eligibility: 21JAN2021-31DEC2025
  - Period of observation: 21JAN2021-28FEB2026

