#### 6.3.2.3. Persistence

Persistence will be measured as time on CAB+RPV LA regimen (months, continuous) as well as the number and proportion of PWH receiving CAB+RPV LA regimen at study end.

Among PWH still receiving CAB+RPV LA regimen at study end, time on CAB+RPV LA will be reported (months, continuous).

Among PWH who discontinued CAB+RPV LA regimen at any point during follow-up, time receiving CAB+RPV regimen prior to discontinuation (months, continuous) will be reported. Among discontinuers with ≥1 VL available during follow-up, viral load at discontinuation will be assessed (VL <200 copies/mL vs. ≥200 copies/mL).

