#### 6.3.2.4. Discontinuation

Discontinuation will be defined as >67 days after last injection (monthly dosing) or >127 days after last injection (every other month dosing).

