# 6.7. \*Data analysis

# 6.7.1. Primary Analysis

## 6.7.1.1. Main Analytical approach

Baseline characteristics and outcomes will be described using counts and absolute and relative frequencies for categorical variables and medians with interquartile ranges (IQR) for continuous variables. For outcomes assessed at any point during follow-up, incidence rates will be estimated using unadjusted Poisson regression, accounting for person-time since index (i.e., first CAB+RPV LA injection).

Analyses will be stratified by viral load (<50 copies/mL vs. ≥50 copies/mL), BMI (<30 kg/m² vs. ≥30 kg/m²), age (18-50, 50-64, ≥65 years), race/ethnicity (non-Hispanic Black, Hispanic, non-Hispanic White), and sex/race (non-Hispanic Black men, Hispanic men, Black women) strata at first CAB+RPV LA injections as sample size allows to assess characteristics, adherence, persistence, discontinuation and virologic effectiveness. Other demographic and clinical variables may also be considered for stratification, if relevant.

Factors including age, sex, race, geographic region, BMI, IDU, CD4 count, any comorbidities associated with confirmed virologic failure will be assessed using multiple logistic regression.

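### Stops shortly before each data cut cannot be recognised, so persistence is overstated and the discontinuation rate understated (by roughly 10-20% at Year 3 for every-other-month dosing, under stated assumptions)

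*Protocol*

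**What the plan says.** Protocol section 6.2 (Study Period) sets three analyses. Year 3 has "Period of eligibility: 21JAN2021-31DEC2023" and "Period of observation: 21JAN2021-29FEB2024". Year 4 has "Period of eligibility: 21JAN2021-31DEC2024" and "Period of observation: 21JAN2021-28FEB2025". Year 5 has "Period of eligibility: 21JAN2021-31DEC2025", with observation to 28 February 2026. The censoring criteria in the same section end follow-up at these observation closes.

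Section 6.3.2.4 gives the only definition of the event: "Discontinuation will be defined as >67 days after last injection (monthly dosing) or >127 days after last injection (every other month dosing". It does not state on which day the discontinuation is dated.

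Section 6.3.2.3 reports, besides time on regimen, "the number and proportion of PWH receiving CAB+RPV LA regimen at study end". Section 6.7.1.1 adds that "incidence rates will be estimated using unadjusted Poisson regression, accounting for person-time since index". Section 6.7.1.2 plans no sensitivity analyses. The protocol states neither a look-ahead beyond the cut nor an earlier cut for this outcome.

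**The concern.** The event needs 67 or 127 days of silence before it exists, and the data stop at the cut. A person who had a last injection in November and never returned looks the same at the end of February as a person who is on schedule. Both are counted as receiving the regimen, and both add person-time in which no stop could have been recorded.

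Persistence and discontinuation are primary objective 2, reported at Years 3, 4 and 5. The bias favours the regimen, and a larger cohort does not reduce it. It also reaches the route to confirmed virologic failure that rests on one raised viral load plus discontinuation (section 6.3.2.6).

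**Working it through.** **The protocol's own figure.** Section 6.5 states a maximum 95% Wald interval width of 0.05 for n = 1,843. Check: 2 × 1.96 × √(0.25/1843) = 0.0457, so the half-width is 2.3 points. It serves here only as a yardstick.

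**Dates (section 6.2).** From 31 December to the cut is 60, 59 and 59 days at Years 3, 4 and 5. The eligibility windows, counting both end dates, are 1,075, 1,441 and 1,806 days. More than 127 days means day 128 or later, and 29 February 2024 minus 128 days is 24 October 2023. Any every-other-month last injection after that date cannot become a discontinuation at Year 3 (after 23 October at Years 4 and 5). For monthly dosing the dates are 23, 22 and 22 December.

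**People who can never have the event.** Every-other-month first injections in the last 68, 69 and 69 eligible days qualify. Under uniform entry: 68/1075 = 6.3%, 69/1441 = 4.8%, 69/1806 = 3.8%. For monthly dosing it is 8 or 9 days, under 1%.

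**Model (assumptions, not in the protocol).** Entry is uniform, the stopping rate λ is constant at 10-40 per 100 person-years (PY), there is no other censoring, and no stop is revealed by a recorded switch. Let F be the time from index to cut, L the lag and v = max(F − L, 0). With stops dated at the last injection:

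- expected recorded events = 1 − e^(−λv)
- expected person-time = [1 − e^(−λv)(1 + λv)]/λ + F·e^(−λv)

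Both are averaged over entry dates.

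**Example: every other month, Year 3, λ = 20 per 100 PY.** Events per person are 0.2169 and person-years per person 1.3509. The rate is 0.2169/1.3509 = 16.05 per 100 PY, which is 19.7% too low. Years 4 and 5 give 17.05 and 17.67.

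**From the missed due date.** With assumed injection intervals of 60 and 30 days, the unverifiable lag falls to 127 − 60 = 67 days and 67 − 30 = 37 days. The Year 3 every-other-month rate is then 17.9 (10.3% too low).

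Understatement of the rate over λ = 10-40 per 100 PY:

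| Schedule, origin of the stop | Year 3 | Year 4 | Year 5 |
|---|---|---|---|
| Every other month, last injection | 19-20% | 14-15% | 11-12% |
| Every other month, missed due date | 10-11% | 7-8% | 5-7% |
| Monthly, last injection | 10-11% | 7-8% | 5-7% |
| Monthly, missed due date | 5-6% | about 4% | 3-4% |

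**Proportion on regimen (every other month, Year 3, λ = 20 per 100 PY).** Recorded 78.3% against 73.2% true with the last-injection origin (5 points), and 75.9% against 73.2% with the due-date origin (about 3 points). Both gaps exceed the 2.3-point half-width.

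**Event dated at threshold crossing.** True survival for that event at 12 months is exp[−0.2 × (1 − 127/365.25)] = 0.878, and at 24 months exp[−0.2 × (2 − 127/365.25)] = 0.719. A simulated Kaplan-Meier curve censored at the Year 3 cut gave the same two values. The Poisson rate is 15.2 at Year 3, because each person's first 127 days enter the denominator but cannot contain an event.

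**Accrual shape.** If entry grows at a continuous rate of 1.0 per year (every other month, last-injection dating), reported over true is about 0.67, 0.69 and 0.70 at Years 3, 4 and 5. The level bias is larger, but the difference between years nearly disappears.

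**Check of the remedy.** Counting stops (dated at the last injection) and person-time only to study end minus the lag returns the assumed rate exactly at all three years.

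**The case against.** Four objections carry weight.

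1. *Dating.* Section 6.3.2.4 can be read as placing the event at threshold crossing. On that reading a person inside the window is not yet discontinued, the cut is ordinary right-censoring, and Kaplan-Meier is valid. This stands. A reader might infer that no survival method censored at the cut would help, and that is true only for last-injection dating. It does not rescue the planned analysis, which is a Poisson rate over all person-time plus a proportion at study end.

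2. *Benchmark.* An every-other-month injection is meant to last about two months, so nobody has stopped until the next one is missed. This stands too, and roughly halves the bias. A reader might also set the threshold-dated rate against a last-injection rate and quote an understatement of up to about 27%. That compares two different events and is not an estimation error.

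3. *Cause.* A reader might blame the 59-60 day gap between eligibility and observation close. The gap only adds the 4-6% of every-other-month starters who can never have the event. The main cause is the lag before the cut, which affects everyone, and a wider gap alone would not cure it.

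4. *Scope.* Event dating and confirmation rules often belong in the SAP, which was not available here. But the protocol itself fixes the cut, the threshold, the censoring and the denominator. An SAP remedy would have to depart from them, so this is more than a missing detail. Recorded switches could reveal some stops sooner, but section 6.3.2.4 does not use them.

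**Conclusion.** The point holds. Followed as written, the protocol overstates the proportion on regimen at each cut. It understates the Poisson discontinuation rate when stops are dated at the last injection or at the missed due date. With threshold dating the rate is still diluted, though Kaplan-Meier would be sound.

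For every-other-month dosing a fair range at Year 3 is 10-20% on the rate, and 3-5 points on the proportion on regimen at 20 stops per 100 PY. Monthly dosing is affected about half as much. The sizes rest on uniform entry, a constant stopping rate, assumed injection intervals for the due-date version, and no stops found through recorded switches. None of these is in the protocol, and the real mix of schedules is unknown. The direction does not depend on the values chosen.

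A reader might infer that the reports will show a spurious rise in discontinuation from Year 3 to Year 5. Under uniform entry they would, because the bias is largest at Year 3. Under fast-growing accrual the years barely differ, and the protocol does not say which applies, so a false trend is possible but not established.

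**What to change.** For persistence and discontinuation:

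- State that a stop is dated at the last injection.
- Count stops and person-time only up to study end minus 127 days (every other month) or minus 67 days (monthly), by the schedule in use at the last injection. Because the definition uses a strict inequality, fix whether the day count is 127/67 or 128/68.
- Report the proportion on regimen as of that date, among people who started before it. Use the remaining days only to confirm stops.
- Apply the same rule to the route to confirmed virologic failure that combines one viral load with discontinuation, or report that route separately. Other virologic outcomes keep the full observation period.
- Re-derive Year 3 by the same rule when Years 4 and 5 are reported. Section 3 planned the Year 3 final tables for August 2024, so changing only later years would break comparability.

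The discontinuation thresholds themselves are untouched. The cost is some wording, one derived date and a rerun of Year 3. About 2-4 months of person-time per person leave the persistence analysis, as do the 4-6% of every-other-month starters with no verifiable follow-up.

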#### **Inclusion criteria:**

- People with HIV
- ≥18 years old
- Treatment experienced
- Active in care in OPERA defined as having a clinical encounter in the 24 months prior to 31DEC2023, 31DEC2024, 31DEC2025
- Received a new ART regimen of interest between 21JAN2021 and 31DEC2023, 31DEC2024, 31DEC2025
  - At least one CAB+RPV LA injection or
  - A prescription for a new oral ART regimen recommended by the DHHS guidelines

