#### \*Study Design

This is an observational study utilizing prospectively collected electronic health record (EHR) data obtained from the OPERA® cohort. The study population will include treatment experienced PWH who are 18 years or older, are active in care in OPERA, and received at least one CAB+RPV LA injection between 21JAN2021 and 31DEC2023, 21JAN2021 and 31DEC2024, and 21JAN2021 and 31DEC2025. PWH will be followed from the date of their first CAB+RPV injection until discontinuation of CAB+RPV regimen, death, loss to follow-up (12 months after last clinical contact), or study end (29FEB2024, 28FEB2025, and 28FEB2026).

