#### For Guidelines Recommended Oral ART:

#### Inclusion criteria:

- People with HIV
- ≥18 years old
- Treatment experienced
- Active in care in OPERA defined as having a clinical encounter in the 24 months prior to 31DEC2024, 31DEC2025
- Received a prescription for a new oral ART regimen (recommended by the DHHS guidelines as first-line therapy at the time of analysis)
- Virologically suppressed (VL <50 copies/mL) at start of new oral ART regimen

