#### Index date

Date of first regimen of interest

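### Entry to the cohort depends on an encounter near the data cut, so early starters who die or leave care are deleted instead of being counted or censored, which flatters persistence

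*Protocol*

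**What the plan says.** Section 6.2 and the synopsis population for CAB+RPV LA both require that a person be "Active in care in OPERA defined as having a clinical encounter in the 24 months prior to 31DEC2023, 31DEC2024, 31DEC2025". The synopsis sets the same rule for the oral comparator: "Active in care in OPERA defined as having a clinical encounter in the 24 months prior to 31DEC2024, 31DEC2025".

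The start of treatment is tested over a much longer span: "Received a new ART regimen of interest between 21JAN2021 and 31DEC2023, 31DEC2024, 31DEC2025". The Study Period list pairs one cut with each analysis year: "Period of eligibility: 21JAN2021-31DEC2023" for Year 3, "Period of eligibility: 21JAN2021-31DEC2024" for Year 4 and "Period of eligibility: 21JAN2021-31DEC2025" for Year 5.

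The index date is the "Date of first regimen of interest". The synopsis adds that "PWH will be followed from the date of their first CAB+RPV injection until discontinuation of CAB+RPV regimen", or until death, loss to follow-up or study end. The censoring list in 6.2 names death and loss to follow-up (12 months after the last contact). Section 6.3.2.4 defines discontinuation as a gap of more than 67 or 127 days after the last injection, depending on the dosing schedule.

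Section 6.7.1.2 plans no sensitivity analyses, and the limitations in 6.9 do not mention this selection.

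**The concern.** Eligibility should be settled by what is known at index. Here it is settled at the end of the enrolment window. For someone who started within the last 24 months the index visit itself satisfies the rule, so nothing is lost. For earlier starters the rule asks whether they were seen again, in some cases years later.

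A person who started in 2021 and died, or left care for good, before 31DEC2023 is absent from the Year 5 cohort. Under the follow-up rules that person should contribute time on treatment and then be censored at death. If alive and gone, the person should count as a discontinuation once the injection gap passes the limit. The entry rule removes the person from both numerator and denominator, so the two parts of the protocol cannot both operate as written.

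At stake is primary objective 2: time on regimen, the proportion on regimen at study end, and discontinuation. The period exposed to the rule lengthens with each cut, so a person counted at Year 3 can be missing at Year 5. The oral comparison (secondary objective 3) inherits the rule, and it could act unequally if the two groups differ in visit frequency. The protocol gives no data on that.

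**Working it through.** The protocol states no figure for this exclusion, so there is none to reproduce. Its 24-month window and eligibility dates fix who is exposed; the size needs assumed rates.

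**Exposure to the rule (dates from the Study Period list in 6.2).** Exposed starts run from 21JAN2021 to the cut minus 24 months.
- Year 3: 344 of 1,074 eligibility days = 32% (11.3 months).
- Year 4: 709 of 1,440 = 49% (23.3 months).
- Year 5: 1,074 of 1,805 = 60% (35.3 months).

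**Assumptions, none of them in the protocol.** Stopping while still in care: 10% per year. Leaving care for good, which ends treatment: λ = 3%, 5% or 10% per year. Both are constant hazards. Starts are either uniform over the eligibility period or rise linearly from zero.

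**Share removed.** Let L be the eligibility period and W the exposed part, in years. A starter at time s < W is removed with probability 1 − e^(−λ(W−s)). Averaging over starts:
- uniform: d = [W − (1 − e^(−λW))/λ] / L
- rising: d = [W² − 2W/λ + 2(1 − e^(−λW))/λ²] / L²

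Year 5, uniform, λ = 0.05: W = 1,074/365.25 = 2.940 and L = 1,805/365.25 = 4.942. Then e^(−0.147) = 0.8633, (1 − 0.8633)/0.05 = 2.734, and d = (2.940 − 2.734)/4.942 = 4.2%.

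**Share on regimen at study end.** Nobody removed is on regimen at study end. If the share among all starters is p, the selected cohort therefore shows p/(1 − d), a rise of p·d/(1 − d). With total exit rate k = λ + 0.10 and study end at E years, uniform starts give p = [e^(−k(E−L)) − e^(−kE)]/(kL). For Year 5, E = 1,864/365.25 = 5.103 and k = 0.15, so p = (0.976 − 0.465)/0.741 = 68.9%. The rise is 0.689 × 0.0417/0.9583 = 3.0 points, to 71.9%.

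| Analysis | Starts | Removed at λ = 3 / 5 / 10% | Rise in share on regimen (points) |
|---|---|---|---|
| Year 3 | uniform | 0.4 / 0.7 / 1.5% | 0.4 / 0.6 / 1.1 |
| Year 3 | rising | 0.1 / 0.2 / 0.3% | 0.1 / 0.1 / 0.3 |
| Year 4 | uniform | 1.4 / 2.3 / 4.5% | 1.1 / 1.7 / 3.1 |
| Year 4 | rising | 0.5 / 0.8 / 1.5% | 0.4 / 0.6 / 1.1 |
| Year 5 | uniform | 2.5 / 4.2 / 8.0% | 1.9 / 3.0 / 5.3 |
| Year 5 | rising | 1.0 / 1.7 / 3.2% | 0.8 / 1.3 / 2.4 |

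**Discontinuation rate.** Simulated Year 5 cohorts with uniform starts give a fall from 13.0 to about 12, from 15.0 to about 13.2, and from 20.0 to about 16.5 per 100 person-years at λ = 3, 5 and 10%. This counts every exit from care as a discontinuation. Deaths are censored under 6.2, so the fall is smaller to the extent that exits are deaths.

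**Scale.** At the n of 1,843 in section 6.5, the widest 95% half-width is 1.96 × √(0.25/1,843) = 2.3 points. The Year 5 rise is of that order in several scenarios.

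**Later time points.** The earliest index plus 36 months is 21JAN2024, after the Year 5 window opens on 31DEC2023. Anyone observed on regimen at 36 months or later therefore meets the rule automatically. In simulation none of them was removed.

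**The case against.** The study calls itself descriptive (6.9.1), and the rule requires only one encounter of any kind in the window. Someone may leave and return and still qualify, and people who stop the regimen but stay in care are kept. Each annual analysis is a cumulative update; no comparison between years is planned. If starts rose over time, which is plausible for a new product, the exclusion is well under half its size under uniform starts. All of this stands, and it limits the size. It does not make a post-index entry condition sound.

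The list of three dates could also be read as satisfied by any one window. That would shrink the exclusion but leave it after index, and the Study Period list points to one cut per analysis.

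A reader might infer more than the protocol supports:
- **Virologic effectiveness is inflated.** This holds only if those removed had worse viral loads, and the protocol gives no data on that.
- **The 36- to 60-month results suffer most.** Those time points are set for suppression and confirmed virologic failure in 6.3.2.6. Among people observed on regimen at those times the rule removes no one. An effect would need a cumulative failure proportion or an all-starters denominator, and the protocol does not state the denominator.
- **Everyone removed is a discontinuer.** Deaths are a separate censoring event.

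**Conclusion.** The concern holds for persistence and discontinuation. As written, the active-in-care rule selects early starters on being seen again after index, and it conflicts with the protocol's own handling of death, loss and discontinuation. The direction follows from the definitions: persistence too high, discontinuation too low.

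The size cannot be fixed from the protocol. It rests on the assumed exit rates, constant hazards and accrual pattern. Within the range tried it is small at Year 3 (at most about 1 point in the share on regimen at study end). At Year 5 it reaches about 2-5 points with uniform starts or 1-2.5 points with rising starts. A reader who sets the annual reports side by side could take part of the growing selection for improvement, although the protocol plans no such contrast.

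Bias in suppression and confirmed virologic failure remains possible but unproven. Estimates among people observed on regimen at 36 months or later are unaffected.

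**What to change.** Define active in care at or before the index date, for example as at least one OPERA encounter in the 24 months up to and including index. Use the same definition in both cohorts for the Year 4 and Year 5 analyses. Later death and loss then fall to the censoring list in 6.2, and later gaps in injections to 6.3.2.4. The index injection visit will usually satisfy such a rule for the injectable cohort, so the amendment should say openly that the criterion will then exclude few or none of those starters.

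The Milestones section scheduled the Year 3 tables as final in August 2024. Either re-run them, or report how many people the cut-based rule excluded and note the change of definition.

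The cost is an amended criterion, a changed cohort query and, if chosen, a re-run of Year 3. No new data are needed. Persistence will look slightly less favourable, and direct comparability with tables already produced is lost.

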#### \*Population

## For CAB+RPV LA:

#### Inclusion criteria:

- People with HIV
- $\geq$ 18 years old
- Treatment experienced
- Active in care in OPERA defined as having a clinical encounter in the 24 months prior to 31DEC2023, 31DEC2024, 31DEC2025

ViiV Healthcare Protocol Final 216990 – Amendment 3

• Received at least one CAB+RPV LA injection between 21JAN2021 and 31DEC2023, 31DEC2024, 31DEC2025

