#### 6.3. \*Variables

#### 6.3.1. Exposure definitions

Exposure is defined as receiving CAB+RPV LA injectable regimen or an oral ART regimen.

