#### 6.4. \*Data source

The OPERA® clinical cohort is a multi-site observational database built from the complete patient health records managed in EHR systems from more than 400 participating caregivers at 142 separate locations throughout the US (Figure 3). Through their membership in OPERA®, medical practices meet the Centers for Medicare & Medicaid Services (CMS) Merit-based Incentive Payment System (MIPS) Incentive Program for Integration with a Specialized Registry. OPERA®-participating physicians and ancillary healthcare providers have documented the care of over 1 million patients in their EHRs, including over 150,000 PWH of which approximately 20% are women, representing 13% of all the PWH linked to care in the US. The OPERA® database is refreshed from these EHR systems at each clinic daily providing up-to-date data for both clinicians and researchers. In total, there are more than 13 million documented prospective visits in the EHR systems for PWH and 4.5 million prescriptions written for ART medications. The average years of follow-up (years of documenting patient visits prospectively in the EHR) for PWH in OPERA® is 5.6 years and there are over 30,000 PWH who have ten years or more of follow-up.

Figure 1. United States Map of OPERA® HIV+ Population and Centers for

Disease Control (CDC) State-by-State Estimates (2017)

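### Objective 3 compares a cohort that enters on an administered injection with one that enters on a prescription, so people who never start can sit only in the oral cohort, and the direction of the bias depends on how they are scored

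*Protocol*

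**What the plan says.** Section 6.2 of the protocol opens its entry rule with a common stem, "Received a new ART regimen of interest between 21JAN2021 and 31DEC2023, 31DEC2024, 31DEC2025", and then gives each cohort its own qualifying event. For the injectable it is "At least one CAB+RPV LA injection or"; for the comparator it is "A prescription for a new oral ART regimen recommended by the DHHS guidelines". The synopsis (Population) draws the same line: "Received at least one CAB+RPV LA injection between 21JAN2021 and 31DEC2023, 31DEC2024, 31DEC2025" against "Received a prescription for a new oral ART regimen".

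Three other places bear on this:

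- Section 6.3.1: "Exposure is defined as receiving CAB+RPV LA injectable regimen or an oral ART regimen". This speaks of receipt but gives no rule for establishing that an oral regimen was begun.
- Section 6.2, Index date: one generic rule, the date of the first qualifying regimen, for both cohorts. The synopsis (Study Design) starts injectable follow-up at the first injection and gives no counterpart for oral ART.
- Section 5, secondary objective 3: baseline characteristics and four treatment outcomes are compared "between oral ART and CAB+RPV LA use in PWH at Year 4 and Year 5 of availability".

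Section 6.7.1.2 plans no sensitivity analysis, and section 6.9 does not mention the difference in entry events.

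**The concern.** An administered dose is a later and stricter step than a written order. Someone ordered CAB+RPV LA who never attends for the injection is outside the study. Someone prescribed a new oral regimen who never fills or takes it meets the oral criterion and, on the natural reading of the index rule, is followed from the prescription date. Attrition between order and first dose is thus removed from one cohort and left in the other.

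At stake is the between-cohort contrast in objective 3. Adjustment for the baseline covariates in section 6.3.3.1 would not cure it: those covariates neither identify the non-starters in the oral cohort nor restore the missing ones to the injectable cohort. Because the entry events are set in the protocol's inclusion criteria, an analysis plan that follows them inherits the problem.

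**Working it through.** The protocol states no figure on this point, so there is nothing to reproduce. The check is whether unequal entry alone creates a difference when starters in both cohorts do equally well.

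**Inputs.** All are assumptions; the protocol gives none of them.

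- x = share of oral prescriptions never started: 2%, 5%, 10%.
- d = 12-month discontinuation among true starters, equal in both cohorts: 10% or 20%.
- k = share of non-starters whom the oral scoring rule records as discontinued. Section 6.3.2.4 defines discontinuation by days since last injection only, so k cannot be read from the protocol.

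**Discontinuation.** Observed oral rate = (1 - x)d + xk. The injectable cohort has no non-starters and shows d. The spurious difference is x(k - d). At k = 1 it is x(1 - d), favouring CAB+RPV LA; at k = 0 it is -xd, favouring oral ART.

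| x | d | Oral rate, k = 1 | Difference (points) | Oral rate, k = 0 | Difference (points) |
|---|---|---|---|---|---|
| 2% | 10% | 11.8% | +1.8 | 9.8% | -0.2 |
| 5% | 10% | 14.5% | +4.5 | 9.5% | -0.5 |
| 10% | 10% | 19.0% | +9.0 | 9.0% | -1.0 |
| 2% | 20% | 21.6% | +1.6 | 19.6% | -0.4 |
| 5% | 20% | 24.0% | +4.0 | 19.0% | -1.0 |
| 10% | 20% | 28.0% | +8.0 | 18.0% | -2.0 |

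The sign changes at k = d.

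For scale, section 6.5 gives a maximum confidence-interval width of 0.05 at n = 1,843, so at most about 2.5 points either side of a single proportion. With x = 5% and k = 1, the 4.0-4.5 points exceed that half-width.

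**Adherence.** Section 6.3.2.5 counts missed and late injections, so there is no oral measure to put numbers into. Direction again depends on scoring.

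**Suppression.** Assume 95% among starters in both cohorts, x = 5%, and non-starters kept in follow-up with suppression s. Observed oral = 0.95 × 95% + 0.05 × s.

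- s = 70%: 93.75%, 1.25 points in favour of CAB+RPV LA.
- s = 95%: 95.00%, no difference.
- s = 98% (a working prior regimen continued): 95.15%, 0.15 points in favour of oral ART.

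**Confirmed virologic failure.** Assume 1% among starters, x = 5%, and failure c among non-starters. Observed oral = 0.95 × 1% + 0.05 × c.

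- c = 10%: 1.45%, favours CAB+RPV LA.
- c = 0%: 0.95%, favours oral ART.

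If non-starters are instead scored as discontinued at once, the censoring rule in section 6.2 ends their follow-up and they add little to either virologic outcome.

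**With aligned entry.** If both cohorts entered on evidence of a first dose, x would be 0 and every difference above would vanish.

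**The case against.** The strongest reply is that the sign is not established. A reader might infer that the rule favours CAB+RPV LA on all four outcomes. The protocol does not support that. Discontinuation and adherence are defined for injections only, so it is unknown here whether an unfilled oral prescription would be scored as an early stop or as continued use; under the second scoring the bias runs towards oral ART. For the virologic outcomes, oral entrants are treatment experienced and, by the synopsis, suppressed when the new regimen starts. One who never switches may simply stay on a regimen that works, so there is no reason to presume more viral loads of 200 copies/mL or above. This part of the reply stands.

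It can also be said that the protocol speaks of receiving a regimen, and that "4.5 million prescriptions written for ART medications" in section 6.4 describes the volume of the database, not how oral starts are ascertained. That is fair: it does not show that start dates or medication-list entries are absent. But the only operational entry criterion for oral ART remains a prescription, and nothing in the protocol adds evidence of use.

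Finally, the point touches one secondary objective. That limits its weight without removing it.

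**Conclusion.** The asymmetry is real and fixed in the eligibility criteria: people who never start can enter the oral cohort and cannot enter the injectable cohort. The objective 3 comparison is therefore not made from a common step, and the protocol plans no analysis that would show how much this matters.

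The size cannot be computed from the protocol. Under the assumed ranges, spurious oral discontinuation lies between +1.6 and +9.0 points if non-starters count as discontinued, and between -0.2 and -2.0 points if they appear persistent. A tilt towards CAB+RPV LA on persistence and adherence is plausible under the first scoring but is not a property of the design as written. For suppression and confirmed virologic failure the effect may be adverse, null or reversed. The primary objectives, which describe CAB+RPV LA users alone, are unaffected.

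**What to change.** Keep the main comparison as planned and make three changes for objective 3.

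1. In section 6.7.1.2, replace the statement that there are no sensitivity analyses with one that applies the same evidence-of-use requirement to both cohorts: for example, a second injection for CAB+RPV LA, and a second prescription or a later active-medication entry for oral ART. Eligibility and follow-up start at that date in both. Applying the requirement to oral users alone would not do: it would remove early oral stoppers while keeping early injectable stoppers, and so create a new asymmetry. Report the time from first record to the evidence date by cohort, since the two may differ.
2. Where CAB+RPV LA orders are recorded, report the number ordered but never injected. The protocol does not show that such orders are held reliably, so this should not carry the main analysis.
3. State the difference in entry events in section 6.9, including that its direction depends on how oral non-starters are scored.

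The cost is one added analysis of records of the kind the cohort already uses, and a few lines of text. The added analysis is smaller and says nothing about the earliest discontinuations in either cohort, which is why it should accompany the main comparison and not replace it.
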